16.7 Qualitative assessments

Researchers at the University of Bristol will collect data for the QuinteT Recruitment Intervention as detailed in sections 10 and 21.6.

16.8 Withdrawal

Withdrawal of consent means that a participant has expressed a wish to withdraw from the study altogether, or from certain aspects of the study only. The type of withdrawal will be collected on the CRF labelled 'Withdrawal'.

Participants may also be withdrawn from the study (or aspects of the study) by their clinician if they believe the participant needs to be withdrawn.

PART_Protocol_V3.0_15May2024_Clean.docx Page **49** of **77**

The Withdrawal CRF should be completed to document the reasons for withdrawal, and state who made the decision to withdraw. Discussions and decisions regarding withdrawal should be documented in the participant's medical notes. Investigators should continue to follow-up any SAEs and should continue to report any SAEs to resolution in the CRF in accordance with the safety reporting section.

Where a participant expresses a wish to withdraw from the study, the study team will determine which aspect(s) of the study the participant wishes to withdraw from; all other aspects of the study/follow-up will be continued.

The aspects of the study that the participant may request to withdraw from are as follows:

- No longer willing to receive study intervention
- No longer willing to complete study questionnaires
 - This refers to the health-related quality of life questionnaires and health care use questionnaires sent directly to participants by the study office
- No longer willing to take part in qualitative aspects of study
 - This refers to the interview for the QuinteT Recruitment Intervention/ the "Information Study"
- No longer willing to provide study tissue samples
 - This refers to any follow-up biopsies
- No longer willing to have study MRIs
- No longer willing to attend study visits
- No longer willing to be contacted by the research team to obtain CRF/outcome data
- No longer willing to have standard of care data from the medical record provided to the study
- No longer willing for standard of care data from Health data providers e.g. NHS digital, to be provided to the study

Where a participant wishes to withdraw from all aspects of study participation detailed above, this will be recorded on the Withdrawal CRF as full withdrawal.

Completion of the Withdrawal CRF will trigger a notification to the Study Office. Appropriate action will be taken by the study teams (centrally at the study office and by the local research team at each participating site) to ensure compliance with the participant's withdrawal request. This may include marking future CRFs as not applicable and ensuring any relevant communications which the participant had consented to receive regarding their participation are no longer sent.

Data collected up to the point of withdrawal will be used in the study analysis.

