7.7.1 Recruitment in the PART feasibility study

Recruitment is often challenging because of difficulties in explaining and justifying the concepts inherent in the trial design (such as randomisation and uncertainty) to patients (31). The QuinteT Recruitment Intervention (QRI) methodology was first developed to address such problems encountered with recruitment to the ProtecT trial, and QRIs have since been successfully integrated within 30 RCTs (32). We included an integrated QRI in the PART Feasibility Study to understand the recruitment process in the clinical centres and gathered evidence about the origin of difficulties as they occurred (using standard and novel qualitative research methods), and then produced rapid plans to address the recruitment difficulties in close collaboration with the Chief Investigator (CI), Trial Management Group (TMG) and Clinical Trials Unit (CTU). This process enabled the research team to understand and then overcome recruitment challenges (33).

In the PART Feasibility Study, five centres opened to recruitment between January and November 2015. In total, 236 patients (out of 329 screened individuals) were identified as eligible to participate by 31st March 2017, and 82 patients agreed to be randomised by 4th May 2017. The QRI findings showed that there was strong support for PART among recruiters. However, many had not previously been involved in RCTs, and in the early part of the PART Feasibility Study they found it challenging to explain aspects of the study, with some holding preconceptions about which treatment was preferable for patients and therefore finding it difficult to maintain equipoise. This meant that some clinicians were not comfortable approaching all eligible patients, and when the study was discussed, biases were conveyed through the use of particular terminology, poorly balanced information and treatment recommendations. The issues identified are common within many RCTs (31). Following the identification of these recruitment issues, the QRI team developed tailored strategies to optimise recruitment, including group training, individual feedback and 'tips' documents. The recruitment rate increased from 15/75 eligible (20%) (January-November 2015) to 67/161 (42%) (December 2015 to March 2017), and recruitment was achieved in four centres (with a clear understanding as to why it was not possible in the one other centre).

PART_Protocol_V3.0_15May2024_Clean.docx Page **20** of **77**

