19.4 Description of Statistical Methods

The primary analysis will be performed according to the Intention-To-Treat principle. Treatment failure will be compared between radical treatment and PA treatment using survival analysis techniques. Statistical significance between treatment groups will be assessed using log rank methods, and Kaplan-Meier survival curves will be used for graphical representation. Patients without treatment failure will be censored at time of death or time of last follow-up. Additional supporting analyses will be undertaken using Cox proportional hazards regression models adjusting for stratification factors and time from randomisation to start of treatment. Patients without treatment failure will be censored at their last known treatment failure free time.

For PORPUS and the other disease-specific HRQoL outcomes, Mixed Models for Repeated Measures (MMRM) will be used to evaluate differences over time by treatment group. MMRM models will be adjusted for treatment, baseline score, stratification factors, visit and a treatment by visit interaction as fixed effect terms, with patient included as a random effect. Differences between treatment groups will be reported as mean difference with 95% confidence intervals. Absolute and percentage average changes in HRQoL outcomes from baseline assessment will be displayed graphically. HRQoL forms that are returned partially complete will be analysed according to the scoring instructions for each questionnaire. The MMRM analyses will minimise the impact of missing data so the use of multiple imputation or other methods for dealing with missing data is not planned. Survival analysis techniques, as described for the treatment failure primary outcome, will also be used to compare differences between radical treatment and PA treatment for time to disease progression (including metastases), time to disease-specific mortality, and time to all-cause mortality. Patients without

disease progression at time of analysis will be censored at time of death or time of last known alive date.

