19.5 Inclusion in analysis

All analyses will be on an intention-to-treat basis. This means that patients will be analysed as they are randomised irrespective of the treatment actually received. The intention-to-treat population will include all patients who have given their informed consent and for whom there is confirmation of successful allocation of a randomisation number.

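### Section 16.8 protects outcome follow-up when the participant asks to withdraw but not when his clinician withdraws him, so a consenting man can be lost and censored without failure

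*Protocol*

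**What the plan says.** Section 16.8 covers two routes out of the study.

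- **Started by the clinician.** "Participants may also be withdrawn from the study (or aspects of the study) by their clinician", on the sole condition that the clinician believes he needs to be. It lists no grounds and does not separate stopping treatment from stopping follow-up.
- **Started by the participant.** "Where a participant expresses a wish to withdraw from the study, the study team will determine which aspect(s) of the study" he wants to leave, and everything else goes on. A graded list of aspects follows, introduced as those the participant may ask to leave.

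Some provisions are not tied to one route. "The Withdrawal CRF should be completed to document the reasons for withdrawal, and state who made the decision to withdraw". Discussions go in the medical notes, SAEs continue to be followed, and completing the form notifies the Study Office. On data, the section says: "Data collected up to the point of withdrawal will be used in the study analysis".

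Section 15.5 (Table 2) lists site research staff, including the PI, as not blinded. For the failure endpoint, section 19.4 states: "Patients without treatment failure will be censored at time of death or time of last follow-up". A second sentence there censors at the last time a man was known to be failure-free. Neither sentence deals separately with withdrawals. Under section 19.5, "patients will be analysed as they are randomised irrespective of the treatment actually received".

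**The concern.** Log-rank and Cox analyses rely on censoring being unrelated to the risk of failure, given what the model conditions on. Section 16.8 leaves the end of a man's follow-up to the judgement of someone who knows his allocation and may be managing his disease. Under section 8.5, failure can itself be determined through clinical concern or concerning imaging, so the same clinical team can influence both whether failure is recorded and whether observation continues.

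If men are removed when they are doing badly, failures in that arm are under-counted. If they are removed when they are doing well, the men left at risk look worse than the arm as a whole. Either could happen in either arm. PORPUS-P, the other co-primary outcome, is also affected, because questionnaires can stop at the same moment.

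This loss is avoidable. The man has not withdrawn consent, and sections 9 and 9.2 say that PSA tests, imaging and biopsies continue as needed in NHS care.

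**Working it through.** No stated figure decides this point, so the check is mainly textual.

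**Step 1: compare the two routes in 16.8.**

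| | Participant asks | Clinician decides |
|---|---|---|
| Scope | Named aspects, or all | Whole study, or aspects |
| Condition | His wish | Clinician's belief |
| Remaining follow-up continues | Stated | Not stated |
| Graded list applies | Yes | Not stated |
| Reason and decision-maker recorded | Yes | Yes |
| SAE follow-up continues | Yes | Yes |

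The only carry-over stated for clinician-initiated withdrawal is SAE follow-up. None is stated for outcomes.

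**Step 2: follow such a man into the analysis.** Section 19.5 keeps him in his randomised arm. If outcome collection has ended and no failure is recorded, section 19.4 censors him at last follow-up or at his last known failure-free time. Intention-to-treat settles which arm he counts in and does not supply what happened to him afterwards. The sentence in section 16.4 that follow-up continues for the duration of the study follows the text on managing diagnosed failure and on recording further treatment. It does not address a man already withdrawn.

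**Step 3: an illustration of scale, based on assumptions.** Inputs from section 19.2: 400 men per arm less 10% dropout = 360; failure 10% (radical) and 20% (PA). Expected failures are 0.10 × 360 = 36 and 0.20 × 360 = 72. The protocol's hazard ratio reproduces: ln(0.90)/ln(0.80) = 0.1054/0.2231 = 0.4722.

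Suppose k men in one arm are withdrawn just before a failure would have been recorded, and none in the other. As a simplification they stay in the denominator without an event. The observed proportion is (72 − k)/360 in the PA arm or (36 − k)/360 in the radical arm, so each man moves the difference by 1/360 = 0.28 points.

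| k | Lost from PA: observed rates, difference, HR | Lost from radical: observed rates, difference, HR |
|---|---|---|
| 0 | 10.0% v 20.0%, 10.0 points, 0.472 | the same |
| 4 | 10.0% v 18.9%, 8.9 points, 0.503 | 8.9% v 20.0%, 11.1 points, 0.417 |
| 9 | 10.0% v 17.5%, 7.5 points, 0.548 | 7.5% v 20.0%, 12.5 points, 0.349 |
| 18 | 10.0% v 15.0%, 5.0 points, 0.648 | 5.0% v 20.0%, 15.0 points, 0.230 |

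Here HR = ln(1 − radical rate)/ln(1 − PA rate). The values of k are assumptions, and nothing in the protocol suggests any of them. Equal losses of k in both arms would leave the difference at 10 points. All these counts fit inside the dropout allowance of about 40 men per arm, which protects against lost numbers and not against bias.

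**The case against.** The strongest reply is that this is an ordinary discretion clause in a protocol that plainly intends to keep men under observation. Suspected recurrence is not given as a ground for withdrawal. Sections 9.2, 13.2 and 16.4 provide for re-staging and further treatment within the study, and section 19.10 keeps a man who declines a biopsy. A clinician therefore need not withdraw anyone in order to manage a recurrence. Withdrawals are documented with reason and decision-maker and notified to the Study Office. Sites are monitored centrally (22.3), and the DSMC sees data by arm (15.5) and meets at least annually (22.4.2). Partial withdrawal is available. Censoring rules and sensitivity analyses can be left to the SAP.

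Most of this stands, and it rules out several stronger readings that a reader might infer:

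- **That only data up to withdrawal may be used.** The sentence in 16.8 says those data are kept. It does not forbid later collection, and the remark about marking future CRFs not applicable is tied to complying with the participant's own request. It cannot be said that no later outcome data will exist, only that the text does not secure them.
- **That a man may be withdrawn at any time, or because failure is near.** Both are inferred from silence. The text leaves them open and does not show that they will occur.
- **That clinician preference will drive withdrawals.** Section 7.7.1 does report "some holding preconceptions about which treatment was preferable for patients". It concerns recruiters explaining the feasibility study to patients, and goes on to describe training and improved recruitment. It says nothing on withdrawal or outcome recording.
- **That events will be lost from the PA arm, with a calculable loss of power.** Any such figure rests on assumed losses in one arm only.

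What the reply does not answer is the asymmetry in 16.8. Records of who was withdrawn and why allow cases to be counted and examined in sensitivity analyses. They do not restore outcomes that were not collected, and an SAP cannot collect them.

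**Conclusion.** The point holds as a gap in the protocol's follow-up procedure. A man who has not withdrawn consent can be taken out of the whole study on his clinician's belief alone, without the continuation rule that applies when he asks to leave himself, and can then be censored without failure. The censoring may be related to prognosis, in either arm and in either direction. Its frequency is unknown. Under the sizing assumptions each missed failure is worth about 0.28 points on a 10-point difference, so a handful would be tolerable and an imbalance of 9 would shift the estimate by 2.5 points. Closing the gap is a cheap improvement. It is not evidence that the analysis is biased, and it does not bear on the stated power. The gap is separate from the pre-treatment suitability check in section 11.1 and would remain if that section were changed.

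**What to change.** Amend section 16.8 in two sentences:

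1. Clinician-initiated withdrawal applies to the study intervention or to named study procedures, recorded against the same graded list used for participant requests.
2. The rule that the rest of follow-up continues applies to this route too. PSA, pathology, treatment, failure, death and questionnaire data are still collected unless the participant himself withdraws from that aspect.

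Align the Withdrawal CRF so that ending outcome collection can be entered only as the participant's own choice. This leaves clinical decisions about his treatment where they are.

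The cost is a short amendment, a CRF edit and slightly more data entry at sites, largely from routine records.

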16.9 Communication with study participants by the central study team

Participants will be notified to completed study questionnaires by e-mail, or where they have selected to receive postal questionnaires these will be posted to the participant. Participants will receive an initial e-mail and up to two reminder messages. Participants that do not complete their study questionnaires may be telephoned by a member of the central study team to collect outcome data.

17 SAMPLES FOR LABORATORY ANALYSIS

17.1 Overview of study-specific samples

Table 4 provides a summary of all samples required by this study protocol

Sample Type and test(s) to be undertaken	Time point (post-treatment)	Analysis by local Trust lab or other
Blood sample for PSA test for eligibility*	Screening/Baseline	PSA tests will be arranged by sites in accordance with usual care practice and analysed by as per usual NHS practice.
Blood sample for PSA test	6 weeks 3 months 6 months 9 months 12 months 24 months** 36 months**	PSA tests will be arranged by sites in accordance with usual care practice and analysed as per usual NHS practice.
Prostate biopsy (PA arm only)	12 months 36 months** Clinical concern	Analysed by local laboratory

*blood test for PSA will be performed to confirm eligibility if no PSA test has been taken in the previous 120 days.

**[#]24-month and 36-month follow-up of all 800 participants is subject to receipt of additional funding for longer-term follow-up, and may not be collected for all participants. Where the test is standard of care this will be performed as usual outside of the study.

The above samples will be taken and processed by laboratories in accordance with local site practice. This includes labelling of samples with standard patient identifiers. Results will be reported back in the usual way according to local practice and accessed by the site research team. Such samples will be stored, held, reported and subsequently destroyed in accordance with standard local laboratory practice. Where required, data will be recorded within the CRF.

18 SAFETY REPORTING

18.1 Safety reporting period

Safety reporting for each participant will begin from the date of commencement of the randomised allocated treatment and will end when the participant has reached their final main follow-up time point (Participants will be followed-up in the study for as long as the study remains open – for those recruited early in the study this may be for 5 years post-randomisation).

18.2 Definition of Serious Adverse Events

A serious adverse event (SAE) is any untoward medical occurrence that:

- Results in death
- Is life-threatening
- Requires inpatient hospitalisation or prolongation of existing hospitalisation
- Results in persistent or significant disability/incapacity
- Consists of a congenital anomaly or birth defect
- Is otherwise considered medically significant by the Investigator

PART_Protocol_V3.0_15May2024_Clean.docx Page **51** of **77**

Significant medical events are medical events that may jeopardise the participant and may require an intervention to prevent one of the outcomes listed above.

NOTE: The term "life-threatening" in the definition of "serious" refers to an event in which the participant was at risk of death at the time of the event; it does not refer to an event which hypothetically might have caused death if it were more severe.

Seriousness vs severity

A distinction is drawn between serious and severe AEs. Severity is a measure of intensity whereas seriousness is defined using the criteria above. Hence, a severe AE need not necessarily be serious.

18.3 Reporting of Serious Adverse Events (SAEs) from sites to the central study team

Only serious adverse events considered by the site investigator to be related (possibly, probably or definitely) to any of the study procedures and in the opinion of the Principal Investigator are considered unexpected for the study procedure will be collected in the study. Such events must be reported within 24 hours to the central study team using the SAE form within the REDCap study database. Refer to section 18.6 regarding expectedness assessment.

Treatment complications listed in section 18.4 should not be reported on a SAE form unless the complication is (in the opinion of the site investigator) considered more severe in nature than might be expected, or unexpected, for the particular intervention received. For participants undergoing IRE or HIFU treatment, the user manual for the devices should also be referred to when making an assessment of expectedness.

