8.3 Secondary objectives and outcome measures

Objective	Outcome measure	Time point(s) of evaluation of this outcome measure (if applicable)
1. To compare the effect on HRQoL of both treatment arms	HRQoL using standard, validated patient-reported outcome measures (PROMs) questionnaires: IPSS, EQ-5D-5L, EPIC and MAX- PC (Modified 18 item)	Baseline, 6wks post- treatment and 3mths, 6mths, 12mths post-randomisation, thereafter every 12 months until the end of the study.
2.To compare the effect on health care resource	Health care resource utilisation and cost-effectiveness in terms	Baseline, 3mths, 6mths, 12mths post-randomisation,

		· · · · · · · · · · · · · · · · · · ·
utilisation of both treatment arms	of cost per quality-adjusted life year (QALY)	thereafter every 12 months until the end of the study.
3.To compare the short and medium term serious adverse events related to treatments in both treatment arms	Short, medium and long-term serious adverse events related to treatments	Short term: 31 days Medium term: 3 years
4.To determine the proportion of patients needing repeat partial ablation treatment	Proportion of patients needing repeat PA treatment in the PA group	Documentation of the need for repeat PA treatment in the PA group – at 1 year post- treatment and 3 years post- treatment (for those that reach this time point in the study's lifetime)
5.To evaluate the accuracy of current mpMRI imaging and biopsy protocols in determining suitability of patients for PA	The proportion of prostatectomy patients who develop high-risk disease or bilateral intermediate disease	After histopathological evaluation (only in men who have had RP, including salvage RP)
6.To determine disease progression beyond the prostate, including local spread and development of metastases	Time to disease progression (including local and distal recurrence)	At a minimum 12 months post-randomisation follow-up of the last recruited participant, but will be longer for those recruited early in the study.
7.To determine medium-term disease-specific and overall mortality	Time to disease-specific and overall mortality	At a minimum 12 months post-randomisation follow-up of the last recruited participant, but will be longer for those recruited early in the study.

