9.2 Collection of outcome data and follow-up assessments

Participants will undergo research specific visits and receive communications from the PART study team to collect outcome data.

Participants will subsequently be followed up in clinic approximately **six weeks post-operatively** and **three-monthly** post-treatment in the first year, and then approximately every **6 months** as per routine NHS care for up to 5 years post-randomisation depending upon when they are recruited into the study. If, at any point, disease progression is suspected, the patient will be re-staged as per NHS standard care.

Participants receiving PA will be required to attend in-person follow-up clinic visits for mpMRI at 1 week, 6 months, 12 months and 36 months[#] post- treatment and for prostate biopsies at 12 months and 36 months[#] (targeted and/or systematic, depending on mpMRI result).

Participants will be sent HRQoL questionnaires (PORPUS, IPSS, EPIC, EQ-5D-5L, and MAX-PC (modified 18 item)), and health care use questionnaires to complete electronically (a postal option will also be made available where required) at 6 weeks post-treatment and at 3 months, 6 months, 12 months, 24 months[#] and 36 months[#] post- randomisation.

Treatment complications and unexpected serious adverse events related to the study intervention will be collected using a combination of medical notes review, Health Care Use Questionnaire review and asking patients at follow-up appointments, and/or when a member of the research team becomes aware that a serious adverse event has occurred.

For participants who have undergone treatment using PA, additional imaging and repeat biopsies could also be triggered by a rise in PSA of at least 50% over a period of 12 months, or due to clinical concern.

Refer to section 16 for full details of outcome data collection and follow-up assessments.

[#]24-month and 36-month follow-up of all 800 participants is subject to receipt of additional funding for longer-term follow-up, and may not be collected for all participants. These participants will continue with standard-of-care NHS follow-up beyond the time duration of the study. Any patients with less than 3 years 'on study' follow up will continue to receive necessary PSA tests, MRI and other imaging, and prostate biopsy as necessary, and/or any additional investigations or treatment, in NHS standard of care pathways beyond the timescale of this study.

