18.6 Assessment of SAEs by the Principal Investigator (or delegate)

The Principal Investigator (or delegated individual) is responsible for assessing all reported serious adverse events for reason for seriousness, causality and expectedness.

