18.6.2 Expectedness

The Principal Investigator (or delegated individual) is responsible for assessing all serious adverse events for reason for causality. Only serious adverse events considered by the site investigator to be related (possibly, probably or definitely) to any of the study procedures should be reported to the CI or nominated person (NP) in the CTU. Such events must be reported within 24 hours to the central study team using the SAE form within the REDCap study database.

Assessment of expectedness will be made by the CI or NP. An unexpected event is not expected for the study intervention and is not listed in the treatment complications below. If in doubt, the CI will raise queries with the treating medical practitioner.

Related SAEs, which are in the opinion of the nominated person are considered unexpected for the study procedure will be submitted to the REC within 15 days of the CI/CTU becoming aware of the event, using the HRA report of serious adverse event form.

All intervention/study procedure-related SAEs will be recorded and reported to the REC as part of the annual reports.

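### Sections 18.3 and 9.2 collect only unexpected related SAEs, contradicting 18.6.2 and 18.7 and falling short of secondary outcome 3

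*Protocol*

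**What the plan says.** **The narrow rule.** Protocol section 18.3 sets the scope of SAE collection: "Only serious adverse events considered by the site investigator to be related (possibly, probably or definitely) to any of the study procedures and", continuing directly, "in the opinion of the Principal Investigator are considered unexpected for the study procedure will be collected in the study". Section 9.2 uses the same limit: "Treatment complications and unexpected serious adverse events related to the study intervention will be collected". Section 18.4 sends a fixed list of complications to a separate form in both arms. Those go on an SAE form only if they are more severe than expected, or unexpected, for the treatment given.

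**The wide rule.** Section 18.6.2 makes relatedness the only condition for site reporting. SAEs the site considers related "to any of the study procedures should be reported to the CI or nominated person (NP) in the CTU", and then "Assessment of expectedness will be made by the CI or NP". Sections 18.6.2 and 18.7 both promise: "All intervention/study procedure-related SAEs will be recorded and reported to the REC as part of the annual reports".

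**Who judges expectedness.** Section 18.6 gives it to the principal investigator or delegate, who "is responsible for assessing all reported serious adverse events for reason for seriousness, causality and expectedness". Section 18.3 agrees with that; section 18.6.2 does not.

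**What the data are for.** Secondary objective 3 in section 8.3 is "To compare the short and medium term serious adverse events related to treatments in both treatment arms", with short term set at 31 days and medium term at 3 years. Neither the objective nor its outcome measure is confined to unexpected events.

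**The concern.** Two sites could each follow a section of the protocol correctly and send different data. A site working from 18.3 withholds a related SAE that it considers expected. A site working from 18.6.2 reports it and leaves expectedness to the centre. The commitment to record all related SAEs can be met only by the second reading.

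The consequence reaches a stated outcome. Outcome 3 compares treatment-related SAEs between arms, and a reduced side-effect profile is part of the trial's aim (section 8.1). Events screened out at site cannot be restored by any method in an analysis plan.

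The filter may also not act equally in the two arms. Section 18.3 ties expectedness to the treatment the participant received and adds the device user manuals as a reference for IRE and HIFU only. The site staff who make the judgement know the allocation (section 15.5, Table 2).

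**Working it through.** The protocol gives no figure here to reproduce, so the check is mainly a comparison of sections.

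**1. The rules side by side**

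| Section | Which SAEs | Who judges expectedness |
|---|---|---|
| 9.2 | Related and unexpected, plus treatment complications | Not stated |
| 18.3 | Related and unexpected | Principal investigator |
| 18.6 | All reported SAEs are assessed | Principal investigator or delegate |
| 18.6.2 | All related are reported by sites and recorded | Chief investigator or nominated person |
| 18.7 | All related are recorded | Chief investigator confirms |
| 8.3, outcome 3 | Treatment-related, no expectedness limit | Not applicable |

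The first two rows cannot be reconciled with the last three on scope. Sections 18.3 and 18.6 cannot be reconciled with 18.6.2 on who judges.

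**2. What the 18.4 form catches.** It lists 8 + 5 = 13 event types. The first eight count only from the procedure to 31 days afterwards. The other five count at any time in follow-up.

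**3. What is left without a form under 18.3.** Take a related SAE that the principal investigator judges expected:
- On the list and inside its window: complication form.
- Off the list: no SAE form and no complication form.
- One of the first eight types, after 31 days: no SAE form and no complication form.

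Section 18.6.2 defines an unexpected event as one that is neither expected for the intervention nor on the complications list. An off-list event that is expected for the intervention is therefore not unexpected, so the definition leaves the gap open. As a hypothetical case, section 7.3 names bowel dysfunction as a possible effect of radiotherapy, while the only general bowel item in 18.4 is in the 31-day group. A later admission for it, judged related and expected, would have no form under 18.3.

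**4. Whether the size can be found.** Let u be the share of related SAEs judged unexpected, and l the share of the expected ones that 18.4 catches. The captured share is c = u + (1 − u) × l, and the observed rate is the true rate × c. The protocol gives none of these inputs, so every value below is an assumption.

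Equal true related-SAE rates of 10%, with u = 0.2 in one arm and 0.5 in the other:
- l = 0: c = 0.20 and 0.50, so 2% v 5%, ratio 2.5.
- l = 0.5: c = 0.2 + 0.8 × 0.5 = 0.60 and 0.5 + 0.5 × 0.5 = 0.75, so 6% v 7.5%, ratio 1.25.
- l = 0.75: c = 0.2 + 0.8 × 0.75 = 0.80 and 0.5 + 0.5 × 0.75 = 0.875, so 8% v 8.75%, ratio 1.09.

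The filter can also hide a real difference. True rates of 15% (radical) and 7.5% (partial ablation) with c = 0.30 and 0.60 give 15% × 0.30 = 4.5% and 7.5% × 0.60 = 4.5%.

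The distortion thus runs from slight to large, and in either direction, depending on values that the protocol does not supply.

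**The case against.** The strongest reply is that the protocol also contains the right rule. Sections 18.6.2 and 18.7 have all related SAEs recorded, so loss of data is not established; it follows only where sites act on 18.3 or 9.2. This stands, and the conclusion is worded conditionally. It does not remove the conflict, because 18.3 is the section headed as the site reporting instruction.

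A second reply is that expected harms have been given their own route on purpose. Listed complications go on a dedicated form in both arms. Complications are collected at treatment start, 6 weeks and 3, 6, 9 and 12 months, and at 24 and 36 months where funding allows (section 16.6). The health care use questionnaire also asks about inpatient stays and emergency attendances (section 20.1). This stands in part: the loss is partial and admissions would leave a trace. But the questionnaire is self-reported resource use and is not described as carrying a relatedness judgement. Nor does the protocol say that 18.4 events count towards outcome 3 or are assessed for seriousness.

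Three stronger readings are tempting and are not supported:
- **That the SAE comparison is biased by arm, by a known amount or towards a known arm.** The wording makes arm dependence possible, but neither size nor direction can be derived.
- **That particular off-list events will be missed.** The protocol does not say which events sites will regard as serious, related and expected. Some bleeding, for example, would meet the blood-loss item in 18.4.
- **That the data monitoring committee will act on filtered data.** Its charter is not available, section 22.4.2 has it review all safety aspects, and it recommends while the steering committee decides on termination (section 19.7).

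**Conclusion.** The point holds as an internal contradiction with a consequence for a stated outcome. Sections 18.3 and 9.2 conflict with 18.6.2 and 18.7 on which related SAEs are collected, and 18.3 and 18.6 conflict with 18.6.2 on who judges expectedness. If sites follow 18.3, related SAEs judged expected that are off the 13-item list, or among its first eight items but after 31 days, have no SAE or complication form. Outcome 3 and the annual report would then be incomplete.

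That the loss could differ by arm rests on three features of the text: expectedness specific to the treatment, device manuals as an added reference for IRE and HIFU only, and unblinded site assessors. How much it would differ, and in which direction, is unknown. The text should be corrected early, since events never recorded cannot be recovered at analysis.

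**What to change.** - Amend 18.3 and 9.2 so that sites report every SAE judged related, whatever its expectedness, in line with 18.6.2 and 18.7.
- Amend 18.6 so that expectedness rests with the chief investigator or nominated person, and use it only to decide expedited reporting to the ethics committee. Check the wording of 18.8 against the same rule.
- State in 8.3 that outcome 3 counts all related SAEs plus those 18.4 complications that meet the seriousness criteria in 18.2.

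If the sponsor prefers to keep the narrow collection rule, outcome 3 and the annual-report commitment in 18.6.2 and 18.7 should be restated to match what is collected. That removes the contradiction but gives up the comparison of all related SAEs.

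The cost is a short amendment touching several sections, plus additional SAE forms at sites. The number of extra forms cannot be estimated from the protocol; reporting covers 800 participants, some followed for up to 5 years.
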